14.1.3 Formulation and Preparation

- Precigen will provide the following materials:
 - The concentration of the PRGN-2009 in supplied vials is 5 x 10E11 PU/ml;
 - PRGN-2009 vials (manufactured by ABL) – 1.0 ml/vial (extractable volume; frozen);

- Final formulation buffer (FFB) Diluent vials (manufactured by ABL) – 4.0 ml/vial (frozen); and
- Sterile empty glass vials (manufactured by ALK) for preparing dilutions (if required).

14.1.3.1 Stability and Storage

PRGN-2009 (manufactured by ABL) is provided as a sterile, frozen, injectable liquid that has been aseptically filled into crystal zenith (CZ) vials fitted with a butyl rubber stopper and an aluminum flip-cap seal. PRGN-2009 must be stored in an ultracold freezer in the temperature range of -60 to -90°C. Each vial contains 1.0 ml (extractable volume) of PRGN-2009 at a target concentration of 5×10^{11} PU/ml. Therefore, each vial contains approximately 5×10^{11} PU.

14.1.3.2 Diluent

Final formulation buffer (FFB; manufactured by ABL) will be used as the diluent for PRGN-2009 and will be supplied by Precigen. Diluent is provided as a sterile, frozen, injectable liquid that has been aseptically filled into crystal zenith (CZ) vials fitted with a butyl rubber stopper and an aluminum flip-cap seal. Each vial contains 4.0 ml (extractable volume) of PRGN-2009. NOTE: no other diluents other than FFB should be used with PRGN-2009.

Two different doses of PRGN-2009 will be evaluated during the phase I dose escalation phase of the trial:

- Initial dose: 1×10^{11} PU – A single vial of PRGN-2009 and a single vial of Diluent will be used for dilution and administration of the initial dose of 1×10^{11} PU. See instructions below for preparation of the initial dose.
- Maximum dose: 5×10^{11} PU – A single vial will be used for administration of the maximum dose of 5×10^{11} PU. No pooling of vials will be required. A Diluent vial will not be needed for the 5×10^{11} PU dose.

14.1.4 Pharmacy Preparation

Follow institutional procedures for handling of a BSL-2 organism. Since the PRGN-2009, is provided with a butyl rubber stopper with aluminum flip-tear seal, these materials do not required handling within a biological safety cabinet. Care should be taken to avoid creation of aerosols during syringe withdrawals through the butyl rubber stopper. If institutional policies dictate, the steps involving a syringe transfer should be conducted within a biological safety cabinet. Spills of PRGN-2009 should be decontaminated using a solution of 10% bleach. All materials should be disposed of according to institutional procedures for a BSL-2 organism.

14.1.5 Vaccine Preparation

Thawing – For each subject, a single vial of PRGN-2009 should be removed from the ultracold freezer and rapidly thawed in a 37°C water bath until the contents are just thawed (avoid prolonged exposure of the thawed vial to the 37°C water bath). Once thawed, do not refreeze. After thawing, vials should be wiped down with 70% IPA. Thawed vials of PRGN-2009 can be stored for up to 2 hours at ambient temperature prior to administration. Do not store thawed vials on wet ice or in contact with a cold pack or inside a refrigerator.

Dilution of PRGN-2009 and storage of the diluted product at ambient temperature is addressed in the pharmacy manual, which should be referenced if dilution is required.

Visually inspect the vailed products before use. If the appearance does not match the appearance listed below, contact the manufacturer (Precigen) and quarantine the vial(s) until further guidance is provided. Do not use the product if they appear to be damaged in any way.

- PRGN-2009 should appear to be a clear to slightly opalescent, colorless liquid and should be free of visible particulates.
- FFB should appear to be a clear, colorless liquid and should be free of visible particulates.

Two different doses of PRGN-2009 will be evaluated during the dose escalation phase of the trial:

- Preparation of the 1×10^{11} PU dose - A single vial of PRGN-2009 will be thawed and diluted 1:5 using the Diluent provided by Precigen, prior to administration to a subject as follows. After thawing, 0.4 ml of PRGN-2009 should be aseptically withdrawn from the vial and transferred into an empty sterile glass vial (provided by Precigen) using an appropriately sized sterile syringe. It is permissible to push air into the vial before withdrawing the specified volumes, as long as aerosols are not created. Next, 1.6 ml of thawed Diluent will be aseptically withdrawn from the Diluent vial using an appropriately sized sterile syringe and this volume will be transferred into the glass vial into which the 0.4 ml of PRGN-2009 has been transferred in the previous step. The contents should be gently swirled to thoroughly mix (do not vigorously shake). A volume of 1.0 ml of the diluted PRGN-2009 will then be aseptically withdrawn using an appropriately sized sterile syringe and administered for the initial dose of 1×10^{11} PU. The remaining contents of the PRGN-2009 vial, the remaining contents of the Diluent vial, the glass dilution vial, and used syringes should be discarded as biohazardous waste. The syringe containing PRGN-2009 can be stored at ambient temperature after preparation. The total time for exposure of PRGN-2009 to ambient temperature after thawing the vial is 2 hours, including dilution, syringe filling and administration. Do not store prepared PRGN-2009 syringe on wet ice or in a refrigerator. Also, do not share vials of PRGN-2009 or Diluent between subjects.
- Preparation of the 5×10^{11} PU dose - The top dose of 5×10^{11} PU will be obtained by aseptically withdrawing 1.0 ml of PRGN-2009 from a single thawed vial using an appropriately sized sterile syringe. One ml of the undiluted PRGN-2009 will be administered for the top dose of 5×10^{11} PU. The empty PRGN-2009 vial should be discarded as biohazardous waste. The total time for exposure of PRGN-2009 to ambient temperature after thawing the vial is 2 hours, including syringe filling and administration. Do not store on wet ice or in a refrigerator.

14.1.6 Stability and Storage

PRGN-2009 and Diluent are provided in cardboard cartons containing 10 vials of frozen liquid. Each 10-pack carton is provided within a sealed, labeled Mylar pouch. The sealed pouch is shipped inside a cardboard box that contains dry ice so that the contents will remain frozen during

Abbreviated Title: Combo Immunotx in HPV OPSCC

Version Date: 09.20.2023

shipment. This Mylar pouch protects the vials from direct exposure to dry ice vapors. PRGN-2009 and Diluent will be shipped to the clinical site from SriSai Biopharmaceutical Solutions, Frederick, MD.

- After receipt, the package should be opened and the contents inspected to confirm that a quantity of dry ice remains and that the Mylar pouch is intact. (Report to Precigen any issues observed when receiving and opening a package). The Mylar-enclosed carton of 10 vials should be immediately transferred to an ultracold freezer and stored in the range of -60 to -90°C. This freezer should be appropriately monitored for temperature excursions. Any excursions that occur outside the recommended storage temperature range for PRGN-2009 should be documented and reported to the Sponsor.

The carton can remain within the Mylar pouch until a vial of PRGN-2009 is required for administration to a subject. After the Mylar pouch is opened, the carton should be quickly returned to the ultracold freezer to avoid exposure of PRGN-2009 to ambient temperature. After the pouch is opened it can be disposed of and the cardboard carton can be stored directly within the ultracold freezer. Do not expose unprotected vials (without Mylar pouch) directly to dry ice vapors after opening and removing the pouch.

14.1.7 Incompatibilities

Not available.

14.2 M7824 (IND #19628)

14.2.1 Source / Acquisition and Accountability

M7824 is manufactured and supplied for the trial by EMD Serono Research and Development Institute to Pharmacy. All study interventions will be given at NIH Clinical Center and documented in the electronic medical record. The investigator or designee (e.g., pharmacist) will maintain an ongoing inventory of the investigational product supply according to standard site procedures. The investigational product will be dispensed at the direction of an investigator for administration to a study participant enrolled on the clinical trial. Disposal of expired or unused product will be returned to the manufacturer or disposed of according to standard site procedures based on agreement between the manufacturer and the site.

14.2.2 Toxicity

The immunoglobulin portion of M7824 molecule is identical to avelumab (Bavencio). Respective warnings and precautions for grade 2 or higher immune-mediated pneumonitis, immune-mediated colitis, immune-mediated endocrinopathies, immune-mediated hepatitis) and infusion reactions are included in the prescribing for Bavencio (bavencio.com). Participants will be pre-medicated to prophylax against infusions reactions. The following additionally significant immune-mediated adverse reactions have occurred in less than 1% of 1738 participants treated with BAVENCIO: myocarditis with fatal cases, myositis, psoriasis, arthritis, exfoliative dermatitis, erythema multiforme, pemphigoid, hypopituitarism, uveitis, Guillain-Barré syndrome, and systemic inflammatory response. The above irAEs are all considered an anticipated risk of treatment with M7824 and thus will not be considered DLTs.

In a phase 1, open-label 3+3 dose-escalation study of M7824 in 16 participants, 3 participants experienced grade 3 drug-related adverse events including skin infection secondary to grade 2 bullous pemphigoid, lipase increased, and colitis with associated anemia. There were no grade 4 – 5 treatment related adverse events. Please see table below for details.

Treatment-related adverse events

	3 mg/kg (n = 3)		10 mg/kg (n = 3)		20 mg/kg (n = 7)		Total (n = 16)	
	Any Grade	Grade 3	Any Grade	Grade 3	Any Grade	Grade 3	Any Grade	Grade 3
Participants with any event**	2 (66.7)	1 (33.3)	1 (33.3)	0 (0.0)	4 (57.1)	2 (28.6)	7 (43.8)	3 (18.8)
Anemia					1 (14.3)	1 (14.3)	1 (6.3)	1 (6.3)
Bullous pemphigoid	1 (33.3)						1 (6.3)	
Colitis					1 (14.3)	1 (14.3)	1 (6.3)	1 (6.3)
Dermatitis acneiform			1 (33.3)				1 (6.3)	
Dyspnea exertional***					1 (14.3)		1 (6.3)	
Hyperthyroidism					1 (14.3)		1 (6.3)	
Hypophosphatemia					1 (14.3)		1 (6.3)	
Hypothyroidism			1 (33.3)		1 (14.3)		2 (12.5)	
Infusion-related reaction					1 (14.3)		1 (6.3)	
Keratoacanthoma					1 (14.3)		1 (6.3)	
Lipase increase					1 (14.3)	1 (14.3)	1 (6.3)	1 (6.3)
Nausea	1 (33.3)						1 (6.3)	
Pruritus	1 (33.3)						1 (6.3)	
Rash maculo-papular	1 (33.3)		1 (33.3)				2 (12.5)	
Skin infection	1 (33.3)	1 (33.3)					1 (6.3)	1 (6.3)
Vomiting	1 (33.3)						1 (6.3)	

**There were no treatment-related AEs in the 3 participants treated with 1 mg/kg M7824.

***The differential for this dyspnea was pneumonitis vs. lymphangitic spread of disease (disease progression).

As of August 2017, > 500 participants have been treated with M7824 across multiple solid tumor expansion cohorts. The safety profile is consistent with other monotherapy checkpoint inhibitors, with the exception of keratoacanthomas and cutaneous squamous cell carcinomas which have occurred in approximately 3-5% of participants and are well managed with surgical excision. These lesions have not been a criterion for treatment discontinuation, but thus far have all spontaneously regressed following treatment discontinuation.

In addition, after discussion among NCI investigators on multiple protocols using M7824 bleeding events ranging from low grade gingival bleeding and epistaxis to more serious hemoptysis, GI bleeding and hematuria have been observed. Some of these events can be attributed to bleeding events related to cancer directly. However, there remains the possibility that M7824 may increase the overall risk of bleeding in ways that may not be directly related to direct tumor bleeding. It is hypothesized that this possible increased bleeding risk may be due to TGF beta inhibition which has an effect on angiogenesis. Accordingly, participants will be notified of the same possible risk in the informed consent document for this study (e.g., gum bleeding, nose bleeds, coughing up blood, blood in their urine, or blood in the stool).

Potential risks include anemia, alterations in wound, healing or repair of tissue damage, and embryofetal toxicity.

In addition, at least 2 instances of nodular regenerative hyperplasia have been observed with the use of this agent.

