3 STUDY IMPLEMENTATION

3.1 STUDY DESIGN

Phase I: Recurrent/metastatic HPV associated cancer

- A 3+3 dose escalation design will be used which will evaluate PRGN-2009 (HPV vaccine) at two dose levels (1×10^{11} and 5×10^{11} VP) given as monotherapy followed by an evaluation of the RP2D dose of PRGN-2009 in combination with 1200 mg (RP2D) of M7824.
- Dose escalation will follow the rules as outlined:
 - After completion of enrollment on DL1 of Arm 1A, enrollment to DL2 of Arm 1A will proceed if 0 out of 3 or 1 out of 6 participants in DL1 of Arm 1A experience a DLT.
 - After completion of enrollment on DL2 of Arm 1A, enrollment to Arm 1B will proceed if 0 out of 3 or 1 out of 6 participants in DL2 of Arm 1A experience a DLT.
 - If 2 participants in a given dose level of Arm 1A or Arm 1B experience a DLT, accrual to that arm will be halted.
- There will be a 4-week DLT evaluation period for each dose level.
- There will be a 1-week delay between the first three participants treated on a given dose level.
- All other participants will be enrolled a minimum of six days apart on the phase I portion of the protocol except between the last participant in one dose level and the first participant in the next dose level in which case the DLT period of 4 weeks will be the minimum wait time.
- In addition, Arm 1B will be expanded to a total of 10 evaluable participants to gauge the preliminary efficacy of the combination of PRGN-2009 and M7824 in participants with advanced disease.

[figure not shown]
Schema for Phase I

Phase II: Newly diagnosed stage I (T1,T2 N1)/II/III HPV-positive oropharyngeal cancer and newly diagnosed stage II/III/IVA/IVB HPV-positive sinonasal squamous carcinoma:

- Evaluation of HPV vaccine alone (Arm 2A) as neoadjuvant or induction therapy in HPV-positive oropharyngeal cancer (20 participants), and HPV-SNSCC participants (2 participants).
- After completion of induction immunotherapy participants will be referred back to their home institution for definitive standard of care therapy. At outside institutions, standard of care treatment will be performed and chosen solely by outside providers. NCI investigators will have no role in treatments received at outside institutions.

Schema for Phase II

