Although positive HPV testing will not be required for the phase I or II portion of the protocol prior to enrolling, HPV testing will be offered as an exploratory endpoint and participants testing negative for HPV after enrolling or whose HPV status cannot be confirmed may be replaced with other participants for the primary efficacy analysis. Participants testing negative for HPV after enrolling or whose HPV status cannot be confirmed may continue to receive treatment on study.

3.1.1 Dose Limiting Toxicity (for first 3-6 participants enrolled on Arms 1A and 1B; phase I part of the study):

Dose-limiting toxicity (DLT) will be defined as any one of the following adverse events, possibly attributable to study drugs, that occur within 28 days of the HPV vaccine monotherapy or 28 days of starting the HPV vaccine + M7824 combination therapy:

- Any Grade 3 or higher bleeding episode requiring blood transfusion(s).
- Any Grade 4 or higher adverse drug reactions (ADRs) as defined by CTCAE v5.0 and assessed as possibly related to any agent by the Investigator, except for laboratory values that are asymptomatic or resolve to Grade ≤ 1 or baseline grade within 7 days without medical intervention.
- Any Grade 3 ADRs possibly attributed to any agent except for any of the following:

- Grade 3 flu-like symptoms or fever, as well as associated symptoms of fatigue, headaches, nausea, emesis which can be controlled with conservative medical management.
- Tumor flare phenomenon defined as local pain, irritation, or rash localized at sites of known or suspected tumor.
- Grade 3 Hgb decrease (< 8.0 g/dL) that is clinically manageable with blood transfusions or erythroid growth factor use does not require treatment discontinuation.
- Grade 3 laboratory values that are asymptomatic or resolve to Grade ≤ 1 or baseline grade within 7 days without medical intervention.
- Keratoacanthoma and squamous cell carcinoma of the skin.
- Any endocrinopathy that can be medically managed with hormone replacement
- Any grade 3 adverse drug reaction which can be medically managed with minimal risk to the participants (e.g., placement of a pleural catheter for recurrent inflammatory pleural effusions) and resolves to at least grade one or baseline grade within 72 hours.

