10 STATISTICAL CONSIDERATIONS

10.1 STATISTICAL HYPOTHESIS

10.1.1 Primary Endpoints

10.1.1.1 Phase I:

The primary endpoint of the phase I portion of the study is to determine the recommended phase II dose (RP2D) of PRGN-2009 (HPV vaccine) alone and in combination with M7824.

10.1.1.2 Phase II:

The primary endpoint of the phase II portion of the study is to determine if HPV vaccine alone (Arm 2A) is able to result in a ≥ 2 -fold increase in CD3+ tumor infiltrating T cells post treatment compared with pre-treatment in participants with p16+ oropharyngeal cancer.

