10.4.7 Planned Interim Analyses

Interim assessment of safety will be made based on DLT assessments according to the 3+3 dose escalation design in the phase I portion of the study and the first six participants enrolled on the phase II portion of the study.

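### Arm 1B only: Section 14.2.2 exempts listed immune-related events from DLT status at any grade, the DLT definition in 3.1.1 does not, and no precedence is stated

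*Combined protocol and SAP*

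**What the plan says.** Section 3.1.1 is the titled DLT definition. It applies "for first 3-6 participants enrolled on Arms 1A and 1B" and covers 28 days from the start of treatment. Two of its criteria matter here:

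- Grade 4 or higher: "Any Grade 4 or higher adverse drug reactions (ADRs) as defined by CTCAE v5.0 and assessed as possibly related to any agent". The only exception is for laboratory values that are asymptomatic or settle within 7 days.
- Grade 3: "Any Grade 3 ADRs possibly attributed to any agent except for any of the following". The exceptions form a closed list. Those that can reach an immune-related event are endocrinopathy managed with hormone replacement, certain laboratory values, and a medically manageable event that carries minimal risk "and resolves to at least grade one or baseline grade within 72 hours".

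Section 14.2.2 gives two lists of immune-mediated reactions. The first comes from the avelumab warnings: pneumonitis, colitis, endocrinopathies and hepatitis. The second is a list of rarer reactions that includes myocarditis and myositis. The paragraph ends: "The above irAEs are all considered an anticipated risk of treatment with M7824 and thus will not be considered DLTs". The words grade 2 or higher, attached to the first list, set a floor and not a ceiling.

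The DLT count feeds the stopping rule in 3.1 ("If 2 participants in a given dose level of Arm 1A or Arm 1B experience a DLT, accrual to that arm will be halted"), the Phase I primary endpoint in 10.1.1.1 ("to determine the recommended phase II dose (RP2D) of PRGN-2009 (HPV vaccine) alone and in combination with M7824") and the interim safety review in 10.4.7 ("Interim assessment of safety will be made based on DLT assessments according to the 3+3 dose escalation design").

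**The concern.** The sentence in 14.2.2 is worded as a rule, not as background: it says which events will not count. Applied literally, it removes severe, drug-related immune toxicity from the DLT count of the one arm that receives M7824. These events are foreseen. Table 3 in Section 3.3.5 names both myositis and myocarditis among the important identified risks of M7824.

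At stake is whether the Arm 1B halting rule, and the combination RP2D that depends on it, rest on one definition of a DLT. Two people applying the protocol in good faith could classify the same event differently and reach different accrual decisions.

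**Working it through.** The documents give no operating characteristic for the 3+3 rule, so there is no stated figure to reproduce. The check is a side-by-side reading, followed by one illustration.

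**Step 1. Classify events under each section.** Assume each is possibly related to study drug, falls within 28 days, and occurs in the first 3-6 Arm 1B participants.

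| Event | Under 3.1.1 | Under 14.2.2 |
|---|---|---|
| Non-fatal grade 4 myocarditis | DLT | Not a DLT |
| Symptomatic grade 3 myositis, unresolved at 72 hours | DLT | Not a DLT |
| Grade 3 colitis lasting more than 72 hours | DLT | Not a DLT, if the sentence covers the first list |
| Grade 3 endocrinopathy managed with hormone replacement | Not a DLT | No conflict |
| Manageable, minimal-risk grade 3 event resolved within 72 hours | Not a DLT | No conflict |

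It is unclear whether the sentence in 14.2.2 refers to both lists or only the second. Myocarditis and myositis are on the second list, so the first two rows conflict on either reading.

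**Step 2. Carry this to the decision.** Two events of the kind in the first two rows, in two of the first 3-6 participants, give 2 DLTs and a halt under 3.1.1. They give 0 DLTs and no halt under 14.2.2.

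**Step 3. Illustrate the size.** Let p be the chance per participant of a listed event that meets 3.1.1. With 0/3, or 1/3 followed by 0/3, as the outcomes that avoid a halt:

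P(halt) = 1 − [(1−p)³ + 3p(1−p)² × (1−p)³]

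The documents give no rate for exactly this event. The table in 14.2.2 shows one grade 3 colitis among 16 M7824 participants, so take p = 1/16 = 0.0625 as an assumption:

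- (1−p)³ = 0.9375³ = 0.8240
- 3p(1−p)² = 3 × 0.0625 × 0.8789 = 0.1648
- P(no halt) = 0.8240 + 0.1648 × 0.8240 = 0.9598
- P(halt) = 0.0402, about 4%

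Under 14.2.2 listed events contribute p = 0, so P(halt) from them is 0%.

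**Range.** The exact 95% interval for 1/16 runs from 0.2% to about 30%. At the lower end P(halt) is essentially nil. At p = 0.302 it is 1 − (0.3401 + 0.4414 × 0.3401) = 0.51. One event in 16 participants therefore fixes very little.

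**Limits of the illustration.** Colitis is on the first list, so the example needs the reading in which 14.2.2 covers that list. The table gives neither timing nor duration, so it is not known whether that event would have met 3.1.1. Dosing in that study was by weight, not the flat 1,200 mg used here.

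**Step 4. Check individual protection.** Section 3.3.1 names DLT-defining toxicity as a reason to discontinue, so the label does appear in the individual rule. The same section also has separate grade 4 and grade 3 triggers. The grade 4 trigger covers the myocarditis example, and the grade 3 trigger covers a myositis unresolved at 72 hours. Both participants stop the responsible agent whichever DLT definition is used.

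**The case against.** The best defence is that 3.1.1 plainly governs. It is the titled definition in the study design section, while 14.2.2 is pharmaceutical information. The same paragraph of 14.2.2 says participants will be premedicated, whereas 3.2.2 makes premedication optional, so the paragraph looks like text carried over and never reconciled. This stands as the likely intent. It does not remove the conflict, because no precedence is stated, and it is equally a reason to correct 14.2.2.

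The second defence is that little now turns on the sentence. Table 8 shows 11 participants treated with the combination, against a target of 10 evaluable, and 0 DLTs. Arm 2B was closed before enrolment, Arm 1A and Arm 2A receive no M7824, and under 3.3.3 any death within 30 days not due to progression or accident halts accrual whatever its DLT status. All of this stands, and it keeps the point small.

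A reader might go further the other way and infer that the reported 0 DLTs conceals exempted events, since Table 8 shows 4 grade 3, 2 grade 4 and 1 grade 5 treatment-emergent events in that column. The documents do not support this. None of those events is shown to be immune-related, within 28 days, or in the first 3-6 participants. The table reports no grade 3 or higher event related to PRGN-2009 and no treatment-related SAE. It has no row for grade 3 or higher events related to M7824, so it does not by itself show which definition was used. It is taken from the investigator's brochure, where the answer may already be given.

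A reader might also infer that participants with severe immune toxicity would stay on M7824. Section 3.3.1 does not support that either, as shown in Step 4.

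**Conclusion.** The inconsistency is real and confined to Arm 1B. The same related, non-fatal event is a DLT under 3.1.1 and not under 14.2.2, and two such events would reverse the halting decision. That conclusion rests on the wording alone and holds on either reading of which list is exempted.

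The practical effect is minor. The illustrative difference in halt probability is about 4% against 0%, on an assumed rate from one event in 16 participants and with a very wide range. Individual protection is essentially unchanged. The DLT stage appears to be over, and there is no evidence that the conflict altered the recorded count. What remains is that a primary Phase I safety result should rest on one stated definition, and at present the protocol contains two.

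**What to change.** Replace the last sentence of the first paragraph of 14.2.2 with: *DLTs are defined solely in Section 3.1.1.* If some immune-related events are meant to be exempt, list them in 3.1.1 with the grades to which the exemption applies. Which events these should be is for the sponsor and investigators to decide.

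Then confirm, in the record or the report, that the 0 DLTs in Arm 1B was counted under 3.1.1: related to any agent, within 28 days, in the first 3-6 participants.

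The cost is one sentence in the next amendment and a review of the 28-day events in those 3-6 participants. It needs no new data or participants and changes no Phase II rule.
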